### 8.2. PROVIDE A DETAILED ANALYSIS PLAN

Differences in plasma NfL and tau between healthy neonates and those with adverse outcomes will be assessed by independent samples t tests or Mann–Whitney U tests, depending on distribution.

The area under the curve (AUC) of the receiver operating characteristic (ROC) curve will be calculated to assess the test characteristics of elevated cord blood NfL and tau in the prediction of adverse perinatal outcomes. Outcomes will be selected for ROC analysis if there is a statistically significant difference observed between healthy/diseased

neonates. The threshold elevation will be determined specifically for each outcome of interest, based on the observed difference in biomarker concentrations between groups. We will compare this to the AUC for CTG abnormalities (binary: present/absent) and scalp lactate elevation for the prediction of the same outcomes.

The normal range of plasma NfL and tau for healthy neonates will be established using the value range in which 95% of confirmed healthy neonates fall.

Scalp blood lactate concentrations will be compared to umbilical cord NfL and tau concentrations using linear regression. The correlation between the presence CTG abnormalities and NfL and tau concentrations will be assessed by independent samples t-test or Mann–Whitney U test, depending on distribution

Our initial analyses will be done independently for elective caesarean section deliveries vs. all other deliveries. However, further adjustments to baseline data may be required. Levels of tau and NfL for the above four analyses may be adjusted based on the multivariable regression analysis described below, if some factors (e.g., gestational age) are revealed to likely confound the outcome.

Linear regression models will be used to assess the correlation between gestational age, birth weight, and duration of 2nd stage of labour and plasma NfL/tau. The relationship between mode of delivery and plasma NfL/tau will be compared using independent samples t test or Mann–Whitney U test, depending on distribution. All the aforementioned variables will be combined into a multivariable regression model for the prediction of plasma NfL/tau to increase precision and adjust for confounders.

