## 1.2. RATIONALE FOR PERFORMING THE STUDY

Any approach to reduce the burden of adverse perinatal outcomes would be a major advance. A decision aid that directly measures brain injury could represent a major advance over current indirect approaches, such as measuring CTG or scalp lactate. In the future, we hope to develop a point-of-care NfL and tau measure that may be used as an adjunct or as a replacement to scalp lactate testing of the foetus, for decisions in labour ward regarding the optimal timing of delivery.

Our focus is on improving perinatal outcomes. A better decision-making aid may enhance:

1. De-escalation of care through confirming the baby is healthy
2. Escalation of obstetric care in a vulnerable baby
3. Understanding the treatment needs in neonatology
4. Improving the safety of anaesthetic care

This study will provide feasibility for a district-wide research cohort study of NfL and tau cord blood levels and perinatal outcomes. A Sydney-based NfL-SIMOA service is being developed in Sydney and with academic and industry partners we will develop a point-of-care testing device for use across peripartum units.

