## 7. OUTCOMES

### 7.1. DEFINITION OF OUTCOMES

'Healthy delivery' will denote a neonate that does not require an emergency caesarean section, prolonged resuscitation at birth, admission to the special care baby unit (SCBU) or neonatal intensive care unit, any re-admission to hospital in the 2 weeks following birth, or has any other documented adverse outcomes (including APGAR score of <7 at 5 minutes) or death in the perinatal period. Healthy deliveries will have no serious documented congenital abnormality, growth restriction or other developmental issue. Babies with no antenatal care data available will be assumed to be developmentally healthy unless there are documented perinatal adverse events.

An adverse outcome will be considered as the presence of any of the above. Intrapartum factors (e.g., abnormal foetal scalp blood sample lactate/pH and cardiotocography abnormalities) will also be considered an adverse outcome for the purpose of analyses.

APGAR scores from 1 and 5 minutes after birth will be collected from the medical record

Gestational weight will be obtained by the first recorded weight following birth

Gestational age will be recorded as per the medical record

Duration of the second stage of labour will be defined as the time from full cervical dilatation (as per progress notes) to the documented time of birth

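### The AUC comparison with CTG and scalp lactate is scored partly on emergency caesarean, an outcome those tests help bring about and which precedes the cord sample

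*Protocol*

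**What the plan says.** Section 7.1 of the protocol defines a healthy delivery through "a neonate that does not require an emergency caesarean section, prolonged resuscitation at birth" and several further conditions: unit admission, re-admission, low 5-minute APGAR, death, congenital abnormality and growth restriction. It then states: "An adverse outcome will be considered as the presence of any of the above". Abnormal scalp lactate or pH and CTG abnormalities are added as adverse outcomes for analysis.

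Section 8.2 evaluates raised cord NfL and tau by ROC curve "in the prediction of adverse perinatal outcomes", with a threshold set separately for each outcome. The entry condition is: "Outcomes will be selected for ROC analysis if there is a statistically significant difference observed between healthy/diseased" neonates. The comparison with the existing tests follows: "We will compare this to the AUC for CTG abnormalities (binary: present/absent) and scalp lactate elevation for the prediction of the same outcomes". No component of the section 7.1 definition is left out of it.

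Section 1.2 describes "current indirect approaches, such as measuring CTG or scalp lactate" as what a new decision aid would improve on, and foresees the markers as an adjunct or "as a replacement to scalp lactate testing of the foetus, for decisions in labour ward regarding the optimal timing of delivery". Section 6.1 has midwives collect the cord blood from placentae, and the schedule in section 6.2.1 puts sampling immediately after delivery.

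**The concern.** A fair comparison of two tests needs an outcome that neither test helps to produce. CTG and scalp lactate are read during labour and inform when delivery takes place. Where an abnormal reading leads to an emergency caesarean, the test scores a true positive because someone acted on it, whether or not the baby was injured. NfL and tau cannot earn that credit, because their result does not exist until the baby is born.

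Section 1.2 presents a direct marker of brain injury as a possible advance over CTG and lactate, and this AUC comparison is the only analysis in section 8.2 that scores them all against a common outcome. If part of that outcome is a decision informed by the comparators, a marker that tracks neonatal injury better could still appear worse. A cut-off for predicting emergency caesarean would also describe an event already past when the sample is taken.

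**Working it through.** The protocol gives no AUC, event rate or ROC power, so there is no figure of its own to reproduce. The text settles the direction of the problem. The numbers below only illustrate it, and every input to them is assumed.

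**Order of events.** CTG and lactate (during labour), then the delivery decision, then birth, then the cord sample (section 6.2.1). Emergency caesarean lies after the comparators and before the markers. Growth restriction and congenital abnormality, also in the section 7.1 definition, likewise precede the cord sample.

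**Closed form.** Let s be the share of emergency caesareans triggered by an abnormal CTG. Let b be the probability of an abnormal CTG in all other births and in emergency caesareans done for other reasons. Assume no link between CTG and injury.

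- Sensitivity for emergency caesarean = s + (1 − s)b
- Specificity = 1 − b
- AUC of a binary test = (sensitivity + specificity)/2 = 0.5 + s(1 − b)/2
- s = 0.3, b = 0.4: 0.5 + 0.3 × 0.6/2 = 0.59
- s = 0.7, b = 0.2: 0.5 + 0.7 × 0.8/2 = 0.78
- s = 0: 0.50

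**Simulation of the composite** (300,000 births). A latent injury correlates 0.25 with the CTG trait, 0.5 with the marker and 0.6 with a neonatal outcome of 12% prevalence. CTG is abnormal in 20 to 40%. Emergency caesarean follows an abnormal CTG with probability f, or arises from an unrelated indication in 10%.

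| Outcome scored | CTG AUC | Marker AUC |
|---|---|---|
| Neonatal outcome only | 0.54–0.56 | 0.66 |
| Emergency caesarean, f = 0 | 0.50 | 0.50 |
| Emergency caesarean, f = 0.2–0.6 | 0.63–0.80 | 0.52–0.54 |
| Either of the two, f = 0 | 0.52–0.53 | 0.59 |
| Either of the two, f = 0.2–0.6 | 0.59–0.75 | 0.57–0.59 |
| Either, or CTG abnormality itself | 0.78–0.89 | 0.57–0.58 |

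By construction the marker is the better test of injury. On the composite in the fifth row, CTG draws level at the lowest f and CTG rate, and is ahead elsewhere. With f = 0 the CTG advantage disappears, so it comes from the decision pathway. With CTG abnormal in 30% and f = 0.4, varying the unrelated-indication rate from 5 to 15% leaves CTG ahead on emergency caesarean (0.69–0.79 against 0.52–0.53).

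**Do the plan's safeguards remove it?**

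- Analysing elective caesareans separately leaves emergency caesareans among all other deliveries.
- The significance filter decides whether a comparison is run, not what the adverse group contains. Emergency caesarean stays in the any-component group.
- The optional adjustment draws on a model that includes mode of delivery. With emergency caesarean in the outcome, that risks adjusting for part of the outcome itself.

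**The case against.** The strongest reply has five parts.

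1. *Conditional entry.* Emergency caesarean becomes a ROC outcome in its own right only if NfL or tau differs significantly, which may not happen. This stands for the single outcome. It does not help the composite.

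2. *Causation.* A reader might infer that every emergency caesarean is decided from CTG or lactate. The documents do not say so. Section 1.2 links these tests to the timing of delivery, does not mention caesarean there, and gives no share. Other indications dilute the tilt without removing it.

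3. *Direction of NfL.* A reader might also infer that NfL would score below 0.5 for emergency caesarean because caesarean lowers it. The NfL evidence in sections 1.1 and 8.1 concerns elective caesarean only. The tau study in section 1.1 speaks of caesarean without qualification. Neither establishes lower NfL after emergency caesarean.

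4. *Controls.* If CTG abnormality counts as adverse, as section 7.1 says, the healthy group has no abnormal CTG and the closed form does not match that contrast. This is correct, but specificity is then 1 by definition and the AUC is (1 + sensitivity)/2. Sensitivity runs from 0.3 + 0.7 × 0.2 = 0.44 to 0.7 + 0.3 × 0.4 = 0.82, giving 0.72 to 0.91. The tilt grows, through a second and more direct circularity.

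5. *Purpose.* The primary objective is feasibility, these links are labelled preliminary, and cord NfL may reflect injury before birth, so an association with emergency caesarean is informative. This stands. It argues for reporting the association, not for using it as the yardstick between tests.

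**Conclusion.** The point holds. As written, sections 7.1 and 8.2 score NfL and tau against CTG and scalp lactate on an outcome set that includes emergency caesarean, which the comparators help to bring about and which precedes the cord sample. The comparison favours CTG and lactate on the composite, and on emergency caesarean alone if it passes the filter. An NfL or tau AUC for emergency caesarean is not a prediction.

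The size cannot be derived from the documents. The range of 0.59 to 0.78 for an uninformative CTG rests wholly on assumed s of 0.3 to 0.7 and b of 0.2 to 0.4, and the simulated reversal of ranking rests on assumed correlations and rates. The conclusion requires only that some emergency caesareans follow from CTG or lactate. Inclusion of growth restriction and congenital abnormality is less certain: they follow from the broad definition in section 7.1, but section 3.2 gives developmental abnormalities an objective of their own. The analysis is secondary and exploratory, so this is a change worth making before analysis, not a threat to the primary endpoint.

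**What to change.** In section 8.2:

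- Limit the ROC analysis, the cut-offs and the comparison with CTG and lactate to neonatal outcomes already listed in section 7.1: prolonged resuscitation, 5-minute APGAR below 7, SCBU or NICU admission, re-admission within 2 weeks, and death.
- Keep emergency-caesarean births in the data set and classify them by their neonatal outcome. Whether they are kept or dropped changes every AUC, so this should be stated.
- Do not count CTG or lactate abnormality as an outcome in this comparison.
- Report emergency caesarean, and growth restriction and congenital abnormality if analysed as adverse outcomes, as group differences in NfL and tau with confidence intervals, described as associations.

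The criterion should be that the outcome is not itself decided from CTG or lactate. Requiring that it be judged after the cord sample would not work, because the schedule does not show that sampling precedes resuscitation or the 5-minute score.

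The cost is wording only. The case report form already records these outcomes, though whether resuscitation was prolonged must be taken from its notes field. Fewer events will enter the ROC analysis. Two limitations should be stated. Care is unblinded, so knowledge of the CTG may still influence resuscitation or admission. Section 6.1 also lets category 1 caesareans go unsampled at the midwife's discretion, so the sampled emergency caesareans may be selected.

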### **Intrapartum factors**

Factor	Outcomes
Prelabour rupture of membranes	PROM PROM >24 hours from birth None Not applicable Unknown
Preterm Birth (<37 weeks)	Yes/No/Unknown
Induction of labour	Required Not required Unknown  Notes: (AROM, cervical ripening methods, etc.)

Duration of 1st stage of labour	4. _____ hours/not applicable
Duration of 2nd stage of labour	5. _____ hours/not applicable
Fetal presentation	Cephalic Breech Transverse Oblique Unstable Unknown Fundic/cord presentation
Fetal distress	Yes/No/Unknown  Notes:
Fetal lactate sample + result	Sampled/not sampled/unknown  _____ mmol/L
Cardiotocography abnormalities	Present (Description: _____) Absent Not applicable Unknown
Pain management	Epidural Nitrous oxide Pethidine Other (Description: _____) None Unknown
Anaesthetic complications	Yes/No/Unknown  6. Description: _____
Caesarean section delivery	Category 1 – Reason: Category 2 Category 3

	Category 4 Not applicable Unknown
Uterotonic agent administration	Oxytocin (units) _____ Ergometrine (mg) _____ Syntometrine (units, mg) _____ Misoprostol (mcg) _____ Carboprost (mcg) _____ Carbetocin _____
Post-partum haemorrhage	Yes/no/unknown (text description)
Umbilical cord gas	pH: Base excess: pCO 2 : PO 2 :
Blood loss	_____ mL
Complications	Uterine rupture Umbilical cord prolapse Chorioamnionitis Puerperal sepsis Other (Description: _____) None Unknown

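### The multivariable model combines mode of delivery with second-stage duration, which does not exist for elective caesareans, so an ordinary fit drops them and loses the adjusted elective-versus-laboured contrast

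*Protocol*

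**What the plan says.** Protocol section 8.2 builds the model in three steps.

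- Three continuous variables come first: "Linear regression models will be used to assess the correlation between gestational age, birth weight, and duration of 2" (the sentence continues with the second stage of labour and plasma NfL/tau).
- Mode of delivery follows: "The relationship between mode of delivery and plasma NfL/tau will be compared using independent samples t test or Mann–Whitney U test, depending on distribution".
- All four then enter one model: "All the aforementioned variables will be combined into a multivariable regression model for the prediction of plasma NfL/tau". Its stated aims are better precision and control of confounding.

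The same section gives this model a second use: "Levels of tau and NfL for the above four analyses may be adjusted based on the multivariable regression analysis described below", on condition that some factor, such as gestational age, looks likely to confound.

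Section 7.1 fixes the meaning of the duration variable: "Duration of the second stage of labour will be defined as the time from full cervical dilatation"; the interval ends at birth. Secondary objective 3 (section 3.2) sets elective caesareans against other deliveries that involve a period of labour, so the elective group is the group without labour. In the case report form (Intrapartum factors), the field for second-stage duration reads "5. _____ hours/not applicable".

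**The concern.** A birth that never reaches full dilatation has no second stage. Its duration is not an unobserved value; there is no value to observe. This holds for every elective caesarean, and for every caesarean performed in labour before full dilatation. The named model nevertheless requires a duration for each birth alongside its mode of delivery, and the protocol does not restrict the model to births with a second stage or say how a 'not applicable' entry is to enter it.

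This is the plan's only multivariable model, and its stated purposes are precision and adjustment for confounders. The background (section 1.1) cites inverse correlations of cord NfL with body weight and gestational age, so an elective-versus-laboured contrast adjusted for these two variables is worth having. Section 8.1 also treats elective caesareans as a separate population with its own sample size. A model that loses that group cannot give the adjusted contrast, and it cannot support an adjustment applied to elective births elsewhere.

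**Working it through.** **Inputs**

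- Planned analysable births (section 8.1): 68 laboured and 24 elective caesareans. Enrolled: 80 and 30.
- Assumed IQRs (section 8.1): 17 and 10 pg/mL, with SD = IQR/1.35.
- Covariates (section 8.2): mode of delivery, gestational age, birth weight, second-stage duration.

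**1. The plan's own group sizes**

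n = (1.96 × SD / 3)², rounded up, with 3 pg/mL as the half-width of the interval.

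- Laboured: SD = 17/1.35 = 12.59; (1.96 × 12.59/3)² = 67.7, giving 68.
- Elective: SD = 10/1.35 = 7.41; (1.96 × 7.41/3)² = 23.4, giving 24.

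Both reproduce. Totals: 68 + 24 = 92 analysable and 80 + 30 = 110 enrolled.

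**2. 'Not applicable' treated as missing**

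| | Planned analysable | Enrolled |
|---|---|---|
| All births | 92 | 110 |
| Elective caesareans, no duration | 24 | 30 |
| Share lost | 24/92 = 26% | 30/110 = 27% |
| Rows kept, at most | 68 | 80 |
| Elective caesareans kept | 0 | 0 |

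Among the kept rows the elective indicator is zero throughout. The design matrix (intercept, elective indicator, gestational age, birth weight, duration) has 5 columns and rank 4, so the elective coefficient is not estimable. A finer coding of mode changes nothing here, because the elective level still has no observations.

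First-stage caesareans drop out as well. The protocol gives no figure for them. If they were an assumed 10% to 30% of the laboured group, the expected rows would be 68 × 0.9 = 61 down to 68 × 0.7 = 48, or 80 × 0.9 = 72 down to 80 × 0.7 = 56.

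**3. 'Not applicable' coded as zero hours**

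The model can now be fitted, but the mode coefficient compares an elective caesarean with a laboured birth whose second stage lasts zero hours. An illustrative simulation shows the shift. It used 24 elective and 68 laboured births, all laboured births with a second stage, and these assumptions, none of which come from the protocol: slope 4 pg/mL per hour, mean duration 1 h, residual SD 10 pg/mL, elective effect −5 pg/mL at zero duration. The true overall difference is therefore −5 − 4 × 1 = −9 pg/mL.

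| Specification | Elective coefficient (pg/mL) | Mean SE |
|---|---|---|
| Duration in hours, elective = 0 | −5.0 | 3.0 |
| Duration left out | −9.0 | 2.5 |
| Duration centred at the laboured mean, elective = 0 | −9.0 | 2.4 |

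Plain zero coding thus answers a different question. Centring among births with a second stage recovers the overall contrast, using all 92 births.

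**4. Does separate analysis by stratum avoid the problem?**

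Section 8.2 says that the initial analyses are run separately for elective caesareans and all other deliveries. For this model that does not help. Within the elective stratum duration is undefined for everyone. Within either stratum the elective-versus-laboured term is constant.

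**The case against.** The strongest reply is that the protocol nowhere prescribes a complete-case fit. It names the variables to be combined but not their parameterisation, which can be settled later, and a valid single model exists: an elective indicator plus duration centred among births with a second stage. This stands. A reader might infer that the model as worded must discard the elective group; the documents do not say so. The loss is what an ordinary fit does by default, not something the protocol requires. The point remains because the protocol has fixed the covariate list, and neither of the two obvious ways of fitting that list delivers the adjusted contrast.

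A reader might also infer that zero coding distorts the duration slope by tying it to mode. It does not. With an elective indicator in the model, elective rows set to zero carry no direct information on that slope. With only mode and duration in the simulated model, the zero-coded and laboured-only slopes agree to rounding error; with gestational age and birth weight added they differ by about 0.01 pg/mL per hour or less.

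Nor does the point defeat objectives 3, 6, 7 and 8. Objective 3 asks for a comparison and does not mention adjustment. Its t test or Mann–Whitney test can use every birth with a result. Gestational age and birth weight are defined for all births in their own regressions, and the regression on duration is naturally confined to births that have one. Mode effects among births that reached full dilatation also remain estimable.

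Finally, adjustment of the other analyses is optional and conditional, and those analyses are initially stratified by elective status. This limits the knock-on effect. It does not supply an adjustment that was estimated with elective births in the data.

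**Conclusion.** The concern holds for one secondary analysis: the multivariable model of section 8.2 and any adjustment taken from it. If 'not applicable' is handled as missing, the model keeps at most 68 of 92 planned analysable births (80 of 110 enrolled), none of them elective, and the adjusted elective-versus-laboured contrast is not estimable. With plain zero coding it is estimable but is no longer the overall contrast between the two groups.

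The 26% rests on the planned group sizes, not on observed numbers. The further loss from first-stage caesareans has no figure in the protocol, and the simulated shift from −9.0 to −5.0 pg/mL is illustrative only.

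The primary endpoint, which concerns the confidence interval for mean NfL, is untouched. No recruitment or data collection step is compromised, since the case report form already holds everything needed. The model should be corrected before analysis, but it does not threaten the study: should-fix, not must-fix.

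**What to change.** Amend section 8.2 as follows.

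1. **All births.** Regress NfL and tau on mode of delivery, gestational age and birth weight, without second-stage duration. Use this model for the adjusted mode contrast and for any adjustment of the other analyses.
2. **Births that reached full dilatation.** Estimate the duration effect here, either by adding duration in a second model limited to these births, or by an equivalent nested term in the all-births model. For the nested term, centre duration among births with a second stage, set it to 0 for the others, and give elective and first-stage caesareans their own mode levels.
3. **Handling rule.** State that a 'not applicable' duration is neither imputed nor entered as plain zero hours.

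The cost is a few sentences of analysis wording and one extra model or one recoded term. No new data, participants or study procedures are needed.
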